#### 1.3.2 Delamanid

Systemic exposure is greater when delamanid is taken with food: about 2-fold greater with a standard meal and 4-fold greater with a high-fat meal. Peak plasma concentrations are reached in approximately 4 hours postdose, regardless of food intake. The elimination half-life of delamanid is about 30 to 38 hours, allowing steady-state to be reached after 10 to 14 days of dosing. The terminal-phase elimination half-life ( $t_{1/2,z}$ ) of its major metabolite (DM-6705) is approximately 230 hours, and steady-state is reached by 8 weeks.

The single-dose C-delamanid trial indicated that delamanid and its metabolites were predominantly excreted in the feces, while renal excretion is a negligible pathway for elimination. In vitro data suggest that delamanid is essentially metabolized by albumin, resulting in the formation of the primary metabolite DM-6705, which in turn is metabolized to DM-6704 and DM-6706. In vitro metabolism studies in human liver microsomes suggest limited contribution of CYP isoenzymes to the metabolism of delamanid, although CYP isoenzymes appear to be involved in consecutive metabolism. Eight metabolites have been identified in human plasma following multiple oral doses, though present at low concentrations after 10 to 14 days of dosing, representing all together about 1% to 10% of parent delamanid. Delamanid does not show clinically meaningful induction and/or inhibitory effects on CYP isoenzyme activity. Delamanid binds to all plasma proteins (> 99.5%) and most extensively (> 97%) to albumin and lipoproteins. The primary metabolites DM-6704, DM-6705, and DM-6706 extensively

Protocol 323-201-00003

(> 97%) bind to human serum proteins. Delamanid does not show affinity for red blood cells. Delamanid and metabolite PK parameters do not notably vary with gender or race.

Administration of delamanid has been shown to result in QT interval prolongation, an effect associated with delamanid and its metabolites but is most closely correlated with DM-6705 plasma concentrations. DM-6705 accumulates slowly over time to reach maximal concentrations after 6 to 10 weeks of treatment. The QT interval prolongation increased accordingly and reversed upon discontinuation of treatment.

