### 1.3.3 Bedaquiline

Bedaquiline is a diarylquinoline derivative that inhibits the proton pump of *M.tuberculosis* ATP synthase. After oral administration BDQ  $C_{max}$  are typically achieved at approximately 5 hours post-dose. The  $C_{max}$  and the AUC increased proportionally up to the highest doses studied in healthy volunteers (700 mg single-dose and once daily 400 multiple doses). Administration of BDQ with a standard meal containing increased the relative bioavailability by about 2-fold compared to administration under fasted conditions.

CYP3A4 was the major CYP isoenzyme involved in vitro in the metabolism of bedaquiline and the formation of the N-monodesmethyl metabolite (M2), which is 4 to 6-times less active in terms of antimycobacterial potency. Based on preclinical studies, bedaquiline is mainly eliminated in feces. The urinary excretion of unchanged bedaquiline was < 0.001% of the dose in clinical studies, indicating that renal clearance of unchanged drug is insignificant. After reaching  $C_{max}$ , BDQ concentrations decline tri-exponentially. The mean terminal elimination half-life of BDQ and the M2 is approximately 5.5 months. This long terminal elimination phase likely reflects slow release of bedaquiline and M2 from peripheral tissues.

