gConfirmation of acid-fast bacilli (microscopy from smear  $\geq$  1+) and drug-susceptible TB using any combination of Xpert MTB/RIF, line probe assay, culture, and/or epidemiologic history.

hFor HIV positive subjects who are included in stage 2, HIV testing does not need to be repeated at screening if the HIV positive status has been documented prior to screening (within the last month) and the documentation can be kept with the trial documentation for the required duration. For subjects who are HIV positive, blood samples are to be drawn for CD4 assessment at the local laboratory.

iFemale subjects only.

jPostmenopausal female subjects only.

kSerum chemistry, hematology, urinalysis, and coagulation testing will be performed at screening, Day -1, Day 4 (predose), Day 7 (predose), Day 14 (predose), and Day 20 or at ET.

lVital signs (blood pressure, heart rate, temperature, and respiratory rate) will be assessed at screening and on Day -1, Day 1 (predose and at 1, 2, 4, 8, and 12 hours postdose), Days 2 through 6 (predose and 2 and 4 hours postdose), Day 7 (predose and 1, 2, 4, 8, and 12 hours postdose), Days 8 through 13 (predose and 2 and 4 hours postdose), Day 14 (predose and 1, 2, 4, 8, and 12 hours postdose), and Days 15 through 20 or at ET. **At screening**, blood pressure and heart rate will be taken with the subject in the **supine (performed first) and sitting position** after remaining for  $\geq$  3 minutes in each position and temperature and respiratory rate will be taken with the subject in the supine position. At all other time points, vital signs will be obtained after the subject has been at rest in the supine position for at least 1 minute. Vital signs will be obtained prior to the ECG and PK blood draw at the nominal time points, where applicable. The post-dose vital signs could be performed within 15 minutes earlier than the expected post-dose timepoints.

mStandard 12-lead ECGs will be collected in triplicate (5 minutes apart) at screening and on Day -1, Day 7 (predose), and Day 14 (predose). The ECGs will be recorded after the subject has been supine and at rest for  $\geq$  10 minutes prior to the first ECG and subjects will remain supine through the final ECG. Electrocardiograms will be obtained prior to the PK blood draw and after vital signs at the nominal time points, where applicable.

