#### **3.7.6.4 Standard 12-lead Electrocardiograms**

Standard 12-lead ECGs will be collected in triplicate (5 minutes apart) at the time points presented in the Schedule of Assessments, [Table 3.7-1](#). The mean ECGs of the 3 time points will be utilized to determine subject's eligibility during screening. The ECGs will be collected prior to PK blood draws and after vital signs at the nominal time points, where applicable.

Standard 12-lead ECGs will be recorded after the subject has been supine and at rest for  $\geq 10$  minutes prior to the first ECG and subjects will remain supine through the final ECG. Heart rate, ventricular rate, RR interval, PR interval, QRS duration, and QT intervals will be recorded. The QTcF and corrected QT interval using Bazett's method (QTcB) will be calculated. The 12-lead ECGs will be evaluated at the trial sites to determine the subject's eligibility and to monitor safety during the trial. The principal investigators or designees (licensed physician) will review, sign, and date each ECG reading, noting whether or not any abnormal results are of clinical significance. The ECG will be repeated if any results are considered to be clinically significant. The reviewers must be listed on FDA Form 1572 and the trial site delegation of responsibility form. Electrocardiogram data will be recorded electronically by the central ECG laboratory(ies) and by the trial site(s). Eligibility for the trial will be based on the central ECG report at the screening visit.

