#### **3.7.7.2 Pharmacodynamic Assessments**

Holter monitoring will be performed on Days -1, 1, and 14 as per the Schedule of Assessments, [Table 3.7-1](#).

Overnight sputum specimens will be provided to the microbiological laboratory for sputum culture and Otsuka TB LAM ELISA measurements.

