#### **3.8.3.2 Documenting Reasons for Discontinuation**

All subjects have the right to withdraw and the investigator can discontinue a subject's participation in the trial at any time if medically necessary.

In addition, subjects meeting the following criteria must be withdrawn from the trial (only one reason for discontinuation [the main reason] can be recorded in the eCRF):

- Death
- TB disease relapse or TB disease progression
- Failure to meet inclusion and exclusion criteria
- Lost to follow-up
- Occurrence of QTcF > 500 msec
- Noncompliance with IMP or RHEZ (if confirmed not related to an AE)
- Physician decision (other than AE)
- Pregnancy (see [Section 5.5](#))
- Major protocol deviation (other than noncompliance with IMP or RHEZ)
- Site terminated by sponsor
- Trial terminated by sponsor
- Withdrawal of consent by parent/guardian (if confirmed not related to an AE)
- Withdrawal of consent by subject (if confirmed not related to an AE)

If the subject discontinues IMP or RHEZ due to an AE, the investigator, or other trial personnel, will make every effort to follow the event until it has resolved or stabilized. Follow-up procedures in [Section 3.8.3.1](#) must be followed. Subjects may be replaced, if discontinuations/withdrawals occur, as described in [Section 3.3](#).

Protocol 323-201-00003

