### 9.6 Electrocardiogram Data

Standard 12-lead ECGs will be collected in triplicate (5 minutes apart) at screening and on Day -1, Day 7 (predose), and Day 14 (predose). The ECGs will be recorded after the subject has been supine and at rest for  $\geq 10$  minutes prior to the first ECG and subjects will remain supine through the final ECG. Electrocardiograms will be obtained prior to the PK blood draw and after vital signs at the nominal time points, where applicable.

Heart rate, ventricular rate, RR interval, PR interval, QRS duration, and QT intervals will be recorded. The QTcF and corrected QT interval using Bazett's method (QTcB) will be calculated.

ECGs are available in triplicates at each nominal timepoint, but may appear as a single or duplicate assessment. All (single, duplicate or triplicate) ECGs at each nominal time point will be averaged and the average will be used in descriptive summary statistics and frequency and percentages. Baseline of ECG is defined as the averaged measurement on Day -1. If the measurement from Day -1 is missing, the screening ECG is taken as baseline.

Summary and change from baseline for ECG will be presented for continuous ECG parameters by visit and treatment group.

Incidence and percentage of potentially clinically significant ECG parameters as defined in Appendix 4 will be presented for each treatment group. All post baseline visit till end of study will be included in incidences of significant change or value. For criteria that involves change from baseline, the subject must have a baseline value to be included in the analysis. For absolute criteria the complete Safety Set will be included.

Incidence of potentially clinically significant QT increases will also be summarized by treatment groups.

In summarizing the incidence of abnormalities, a patient must have had an evaluation that met abnormality criteria by the end of trial, i.e. last contact date. Incidence rate is calculated as the number of patients having at least one abnormality within a trial period divided by the number of patients who are both exposed to trial medication and have an on-treatment evaluation within that trial period.

When the ECG is repeated, the last repeat value will be used in the summary for that visit. Unscheduled ECG data will not be summarized in the change from baseline descriptive analysis but will be included in the incidence of clinically relevant table.

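### No 12-lead ECG is scheduled after the last dose or at early termination, although the metabolite the protocol links to QT prolongation outlasts dosing, and SAP 9.6 gives two ECG denominators

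*Protocol*

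**What the plan says.** - **Schedule.** Protocol Table 3.7-1, footnote m, places 12-lead ECGs "at screening and on Day -1, Day 7 (predose), and Day 14 (predose"). Table 3.7.3-1 and SAP 9.6 agree. The ECG row is blank for Day 15, Days 16 to 19 and Day 20/ET. The Day 20/ET list has a targeted examination, weight, vital signs, laboratory tests and a PK sample.
- **Purpose of the 12-lead ECG.** Protocol 3.7.6.4: "The 12-lead ECGs will be evaluated at the trial sites to determine the subject's eligibility and to monitor safety during the trial". It adds: "The ECG will be repeated if any results are considered to be clinically significant".
- **Withdrawal criterion.** Protocol 3.8.3.2 lists "Occurrence of QTcF > 500 msec" and does not name the recording. Section 3.8.3.1 directs discontinued subjects to the ET and follow-up assessments.
- **QT risk.** Protocol 1.3.2 says that delamanid prolongs QT and that the effect correlates most closely with DM-6705 (half-life about 230 h): "DM-6705 accumulates slowly over time to reach maximal concentrations after 6 to 10 weeks of treatment". It puts the delamanid peak at about 4 h. Section 1.3.3 says bedaquiline peaks "are typically achieved at approximately 5 hours post-dose".
- **Holter.** Protocol 3.7.7.2, under pharmacodynamics: "Holter monitoring will be performed on Days -1, 1, and 14 as per the Schedule of Assessments". Sections 6.2 and 6.3 use these data descriptively and for a concentration-QT analysis.
- **Analysis.** SAP 9.6: "All post baseline visit till end of study will be included in incidences of significant change or value". For absolute criteria it takes the whole Safety Set. Later in the same section it divides by exposed patients who also have an on-treatment evaluation.

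**The concern.** Safety is a Stage 2 primary objective, and the protocol itself names a QT effect driven by a slowly eliminated metabolite. The scheduled safety ECGs stop before the last dose is given, while subjects remain in the ward with PK sampling to 144 h. The subjects for whom a closing ECG is most informative, those withdrawn for QTcF or stopping early, are not scheduled to have one at ET. The SAP promises counts to the end of the study, but no scheduled reading exists after Day 14 predose. Depending on which SAP sentence the programmer follows, a subject with no on-treatment ECG is either left out of the rate or counted as free of QTc > 450 or > 500 msec.

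**Working it through.** **Counting the schedule.** There are two on-treatment 12-lead time points, each in triplicate (2 × 3 = 6 tracings). Day 7 predose follows 6 of 14 doses, leaving 8. Day 14 predose follows 13, leaving 1. None is scheduled after the last dose or at ET. Both readings fall about 24 − 4 = 20 h after the previous delamanid peak and 24 − 5 = 19 h after the previous bedaquiline peak.

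**Subjects concerned.** Two Stage 2 arms contain delamanid: 14 + 14 = 28.

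**Reproducing the protocol's own statement.** Section 1.3.2 has DM-6705 at steady state by 8 weeks. Eight weeks is 1344 h, and 1344/230 = 5.84 half-lives, so 1 − 2^(−5.84) = 98.3%. The 230 h figure is consistent with that statement.

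**Where the ECGs fall on the DM-6705 curve.** Inputs from Protocol 1.3.2 are a delamanid half-life of 30 to 38 h and a DM-6705 half-life of 230 h. The model's own assumptions are instant absorption, first-order kinetics and complete conversion. Doses are given at 0, 24, …, 312 h. With kp = ln2/(30 or 38) and km = ln2/230, the amount of metabolite at time t is the sum over doses given of kp/(kp − km) × [exp(−km·u) − exp(−kp·u)], where u is the time since that dose. Average steady state is 1/(24·km).

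| Time (h from first dose) | % of steady state | % of in-trial peak |
|---|---|---|
| Day 7 predose (144) | 26–28 | 45–47 |
| Day 14 predose (312) | 55–56 | 94–95 |
| Peak (346–353) | 58–60 | 100 |
| Day 20 (456) | 48.5–49.5 | 81–85 |
| 14 days after last dose (648) | 28–29 | 46–49 |

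The peak comes 346 − 312 = 34 h to 353 − 312 = 41 h after the last dose. That peak and the decline after it have no scheduled 12-lead ECG.

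**Denominators.** The two SAP rules differ by the number of subjects with no on-treatment ECG. As an illustration only, suppose that in an arm of 14 one subject stops before Day 7 without an ECG and one other exceeds a limit. The rate is then 1/14 = 7.1% under one rule and 1/13 = 7.7% under the other. The numerical effect is small; the problem is that the rule is not fixed.

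**The case against.** The schedule is consistent across both documents, so this is a design choice rather than a slip. Other safeguards exist: exclusion for QTcF > 450 msec, hypokalemia and cardiac disease; chemistry on Days 4, 7, 14 and 20; an inpatient stay to Day 20; nonclinical QTc data before Stage 2; and follow-up of adverse events leading to discontinuation. All of this stands, but none of it places an ECG at ET.

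Several stronger readings are tempting, and the documents do not support them:

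- **That only two ECGs can trigger withdrawal.** The criterion names no recording. Repeat ECGs are required after a clinically significant result, SAP 9.6 counts unscheduled ECGs, and Holters are recorded on Days 1 and 14. Repeat and unscheduled ECGs do need a trigger, however. The Holter has no stated read time and no link to the criterion or to SAP Appendix 4.
- **That the QT risk is not followed over its time course.** Day 14 predose is at 94 to 95% of the modelled in-trial DM-6705 peak, and the 6-to-10-week maximum cannot occur in a 14-day course. The trough argument is also weak for DM-6705, which loses at most 1 − 2^(−24/230) = 7% in 24 h.
- **That QT status is unknown at discharge.** A Day 14 ECG and Holter exist for those who complete dosing.
- **That all 42 Stage 2 subjects on investigational treatment carry the named risk.** Protocol 1.3.3 and 1.4.3 state no QT effect for bedaquiline; 1.4.3 refers to a package insert that is not part of these documents.
- **That SAP 9.6 settles on undercounting.** It contains two rules, so it is unresolved.

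**Conclusion.** The point holds as a cheap improvement. The scheduled safety ECGs end at Day 14 predose and are absent from Day 20/ET. That does not match Protocol 1.3.2, the ET pathway that follows the QTcF criterion in 3.8.3.2, or the SAP's reporting to the end of the study. The size is 28 subjects on delamanid, with modelled DM-6705 at 81 to 85% of its in-trial peak on Day 20. The schedule counts come directly from the documents. The percentages depend on the model assumptions and on the protocol's half-lives, and show where readings fall on an exposure curve; they do not estimate a QT change. Holter partly covers the postdose period on Days 1 and 14. The denominator conflict in SAP 9.6 is a separate defect and needs no model.

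**What to change.** 1. Reconcile the ECG row of Table 3.7-1, footnote m, Table 3.7.3-1 and SAP 9.6 with Protocol 1.3.2 and 3.8.3.2 by including the triplicate 12-lead ECG already in use among the Day 20/ET assessments. By Day 20 subjects on investigational treatment have moved to RHEZ, and SAP Appendix 4 speaks of on-treatment values, so the SAP should say how this reading is reported.
2. In SAP 9.6, keep one denominator for absolute ECG criteria, chosen so that a subject with no on-treatment ECG is not counted as free of QTc > 450 or > 500 msec, and report the number of such subjects per arm.
3. Have the sponsor state which recordings the QTcF > 500 msec criterion refers to, and reconcile the ECG timing with the peak times in Protocol 1.3.2 and 1.3.3. No time, threshold or withdrawal rule is proposed here.

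The cost is a protocol amendment and SAP wording, one more triplicate ECG per inpatient on existing equipment, and possibly a few more QTc flags to review.

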### 3.7.1 General Inpatient Procedures

Subjects will remain either in a seated or semi-recumbent position for the first 4 hours following dosing except during brief periods where protocol-related procedures will be performed. During the 4 hours postdose, restroom visits should be brief (< 10 minutes). Following the 4-hour postdose period, the subjects will be allowed to ambulate, but should not exercise strenuously.

### 3.7.2 Dietary Requirements

During the in-clinic period, meals will include breakfast, lunch, dinner, and an evening snack. On days when subjects are admitted and discharged, not all meals may be provided depending on the time of admission or discharge.

RHEZ will be administered with 240 mL of still (noncarbonated) water 1 hour prior to a meal or 2 hours after a meal. OPC-167832, delamanid, and BDQ (stage 2 only) will be administered with 240 mL of still (noncarbonated) water at room temperature.

### 3.7.3 Schedule of Assessments

Vital signs will be obtained prior to the ECG and PK blood draw at the nominal time points, where applicable. The post-dose vital signs could be performed within 15 minutes earlier than the expected post-dose timepoints. Electrocardiograms will be obtained prior to the PK blood draw and after vital signs at the nominal time points, where applicable.

If a PK blood sample cannot be drawn at the designated time, a window of  $\pm 15$  minutes for each blood draw is acceptable, with the exception of the 0.5 hour draw. The acceptable window for the 0.5 hour draw is + 5 minutes. For all blood draws, the exact time should be recorded. For the delamanid / OPC-167832 and the delamanid / OPC-167832 / BDQ arms, the PK sample will be drawn based on the delamanid dosing.

The 16-hour sputum sampling must be finished prior to the administration of the next day's IMP or RHEZ, if applicable.

Trial days and activities are summarized in [Table 3.7.3-1](#) (Note: activities to be performed throughout the trial are provided in the last row of the table).

Protocol 323-201-00003

Table 3.7.3-1	Trial Days and Activities
Screening (Days –6 to –3) (Screening can be extended up to 7 days [Day –9 to Day –3], if needed)	

Subjects will be screened for up to 4 days prior to the Day –2 assessments. At the screening, the following will be performed:
 
 
• Review trial procedures and information regarding the nature of the trial and obtain informed consent prior to any trial-related procedures.
 
• Admission of subjects to trial site.
 
• Review inclusion and exclusion criteria.
 
• Collect demographic information.
 
• Document medical history.
 
• Measure height and weight and calculate BMI.
 
• Perform a complete physical examination.
 
• Perform a chest x-ray (if a chest x-ray is available that has been taken within 2 weeks prior to screening, which in the opinion of the investigator is a reflection of the subject’s TB status, is of adequate quality, and which can be kept with the trial documentation for the required duration, this x-ray can be used as the screening x-ray).
 
• Perform spot sputum for confirmation of acid-fast bacilli (microscopy from smear <math>\geq 1+</math>) and drug-susceptible TB using any combination of Xpert MTB/RIF, line probe assay, culture, and/or epidemiologic history.
 
• Perform serum hepatitis (HBsAg and anti-HCV) and HIV screen. For HIV positive subjects who are included in stage 2, HIV testing does not need to be repeated at screening for HIV positive subjects if the HIV positive status has been documented within a month prior to screening and the documentation can be kept with the trial documentation for the required duration. For subjects who are HIV positive, blood samples are to be drawn for CD4 assessment at the local laboratory.
 
• Perform urine pregnancy test (female subjects only).
 
• Perform FSH testing (postmenopausal female subjects only).
 
• Perform urine/blood alcohol and urine drug screen.
 
• Collect serum chemistry, hematology, urinalysis, and coagulation clinical laboratory samples.
 
• Assess vital signs (blood pressure, heart rate, temperature, and respiratory rate). Blood pressure and heart rate will be taken with the subject in the supine (performed first) and sitting position after remaining for <math>\geq 3</math> minutes in each position and temperature and respiratory rate will be taken with the subject in the supine position.
 
• Collect a standard 12-lead ECG in triplicate (5 minutes apart). The ECGs will be recorded after the subject has been supine and at rest for <math>\geq 10</math> minutes prior to the first ECG and subjects will remain supine through the final ECG.
 
	
Day –2	

Subjects can proceed with the Day –2 assessments as soon as the screening assessments have been completed. On Day –2, the following will be performed:
 
 
• Start overnight sputum collection for Day –2 sample (approximately 10 mL or more) at approximately 3:00 PM.
 
• Provide meals as necessary.
 
	

Protocol 323-201-00003

Table 3.7.3-1	Trial Days and Activities
Day -1	
On Day -1, the following will be performed:	

 
• End overnight sputum collection (for Day -2 sample) at approximately 7:00 AM. Sputum will be cultured on solid media for quantification of bacterial load and in the MGIT system for TTD determination, and assessed in the LAM assay. Positive MTB isolates will be tested for MIC to OPC-167832 in stages 1 and 2, and for MIC to delamanid in stage 2 only.
 
• Review inclusion and exclusion criteria.
 
• Measure weight.
 
• Perform a complete physical examination.
 
• Collect serum chemistry, hematology, urinalysis, and coagulation clinical laboratory samples.
 
• Assess vital signs (blood pressure, heart rate, temperature, and respiratory rate). Vital signs will be obtained after the subject has been at rest in the supine position for at least 1 minute.
 
• Collect a standard 12-lead ECG in triplicate (5 minutes apart). The ECGs will be recorded after the subject has been supine and at rest for <math>\geq 10</math> minutes prior to the first ECG and subjects will remain supine through the final ECG.
 
• Perform Holter monitoring.
 
• Start overnight sputum collection for Day -1 sample (approximately 10 mL or more) at approximately 3:00 PM.
 
• Provide breakfast, lunch, dinner, and an evening snack.
 
	
Day 1	
On Day 1, the following will be performed:	

 
• End overnight sputum collection (for Day -1 sample) at approximately 7:00 AM. Sputum will be cultured on solid media for quantification of bacterial load and in the MGIT system for TTD determination, and assessed in the LAM assay.
 
• Perform a targeted physical examination at predose and 4 hours postdose. The 4-hour post-dose targeted physical examination could be performed <math>\pm 30</math> minutes after the expected post-dose timepoint.
 
• Assess vital signs (blood pressure, heart rate, temperature, and respiratory rate) at predose and at 1, 2, 4, 8, and 12 hours postdose. Vital signs will be obtained after the subject has been at rest in the supine position for at least 1 minute. The post-dose vital signs could be performed within 15 minutes earlier than the expected post-dose timepoints.
 
• Perform Holter monitoring.
 
• Randomize subjects to a treatment prior to first dosing.
 
• For subjects randomized to OPC-167832 (stage 1) and/or delamanid and/or BDQ (stage 2), collect PK blood samples for OPC-167832 only (stage 1) or OPC-167832, delamanid and its metabolite DM-6705 or BDQ and its metabolite M2 (stage 2) at predose (within 2 hours prior to dosing) and 0.5, 1, 2, 3, 4, 5, 6, 8, and 12 hours postdose.
 
• Administer oral dose of RHEZ or IMP. RHEZ will be administered with 240 mL of still (noncarbonated) water 1 hour prior to a meal or 2 hours after a meal. The IMP will be administered with 240 mL of still (noncarbonated) water at room temperature.
 
• Provide breakfast, lunch, dinner, and an evening snack.
 
	

Protocol 323-201-00003

Table 3.7.3-1	Trial Days and Activities
Day 2	

On Day 2, the following will be performed:
 
 
• Perform a targeted physical examination at predose and 4 hours postdose. The 4-hour post-dose targeted physical examination could be performed <math>\pm</math> 30 minutes after the expected post-dose timepoint.
 
• Assess vital signs (blood pressure, heart rate, temperature, and respiratory rate) at predose and 2 and 4 hours postdose. Vital signs will be obtained after the subject has been at rest in the supine position for at least 1 minute. The post-dose vital signs could be performed within 15 minutes earlier than the expected post-dose timepoints.
 
• For subjects randomized to OPC-167832 (stage 1) and/or delamanid and/or BDQ (stage 2), collect PK blood sample for OPC-167832 only (stage 1) or OPC-167832, delamanid, and its metabolite DM-6705, or BDQ and its metabolite M2 (stage 2) at 24 hours after the Day 1 dose.
 
• Administer oral dose of RHEZ or IMP. RHEZ will be administered with 240 mL of still (noncarbonated) water 1 hour prior to a meal or 2 hours after a meal. The IMP will be administered with 240 mL of still (noncarbonated) water at room temperature.
 
• Start overnight sputum collection for Day 2 sample (approximately 10 mL or more) at approximately 3:00 PM.
 
• Provide breakfast, lunch, dinner, and an evening snack.
 
	
Day 3	

On Day 3, the following will be performed:
 
 
• End overnight sputum collection (for Day 2 sample) at approximately 7:00 AM. Sputum will be cultured on solid media for quantification of bacterial load and in the MGIT system for TTD determination, and assessed in the LAM assay.
 
• Perform a targeted physical examination at predose and 4 hours postdose. The 4-hour post-dose targeted physical examination could be performed <math>\pm</math> 30 minutes after the expected post-dose timepoint.
 
• Assess vital signs (blood pressure, heart rate, temperature, and respiratory rate) at predose and 2 and 4 hours postdose. Vital signs will be obtained after the subject has been at rest in the supine position for at least 1 minute. The post-dose vital signs could be performed within 15 minutes earlier than the expected post-dose timepoints.
 
• Administer oral dose of RHEZ or IMP. RHEZ will be administered with 240 mL of still (noncarbonated) water 1 hour prior to a meal or 2 hours after a meal. The IMP will be administered with 240 mL of still (noncarbonated) water at room temperature.
 
• Provide breakfast, lunch, dinner, and an evening snack.
 
	
Day 4	

On Day 4, the following will be performed:
 
 
• Perform a targeted physical examination at predose and 4 hours postdose. The 4-hour post-dose targeted physical examination could be performed <math>\pm</math> 30 minutes after the expected post-dose timepoint.
 
• Collect serum chemistry, hematology, urinalysis, and coagulation clinical laboratory samples at predose.
 
• Assess vital signs (blood pressure, heart rate, temperature, and respiratory rate) at predose and 2 and 4 hours postdose. Vital signs will be obtained after the subject has been at rest in the supine position for at least 1 minute. The post-dose vital signs could be performed within 15 minutes earlier than the expected post-dose timepoints.
 
• Administer oral dose of RHEZ or IMP. RHEZ will be administered with 240 mL of still (noncarbonated) water 1 hour prior to a meal or 2 hours after a meal. The IMP will be administered with 240 mL of still (noncarbonated) water at room temperature.
 
• Start overnight sputum collection for Day 4 sample (approximately 10 mL or more) at approximately 3:00 PM.
 
• Provide breakfast, lunch, dinner, and an evening snack.
 
	

Protocol 323-201-00003

Table 3.7.3-1	Trial Days and Activities
Days 5 and 6	

On Days 5 and 6, the following will be performed:
 
 
• End overnight sputum collection (for Day 4 sample) at approximately 7:00 AM (Day 5 only). Sputum will be cultured on solid media for quantification of bacterial load and in the MGIT system for TTD determination, and assessed in the LAM assay.
 
• Perform a targeted physical examination at predose and 4 hours postdose. The 4-hour post-dose targeted physical examination could be performed <math>\pm</math> 30 minutes after the expected post-dose timepoint.
 
• Assess vital signs (blood pressure, heart rate, temperature, and respiratory rate) at predose and 2 and 4 hours postdose. Vital signs will be obtained after the subject has been at rest in the supine position for at least 1 minute. The post-dose vital signs could be performed within 15 minutes earlier than the expected post-dose timepoints.
 
• Administer oral dose of RHEZ or IMP. RHEZ will be administered with 240 mL of still (noncarbonated) water 1 hour prior to a meal or 2 hours after a meal. The IMP will be administered with 240 mL of still (noncarbonated) water at room temperature.
 
• Start overnight sputum collection for Day 6 sample (approximately 10 mL or more) at approximately 3:00 PM (Day 6 only).
 
• Provide breakfast, lunch, dinner, and an evening snack.
 
	
Day 7	

On Day 7, the following will be performed:
 
 
• End overnight sputum collection (for Day 6 sample) at approximately 7:00 AM. Sputum will be cultured on solid media for quantification of bacterial load and in the MGIT system for TTD determination, and assessed in the LAM assay.
 
• Measure weight.
 
• Perform a targeted physical examination at predose and 4 hours postdose. The 4-hour post-dose targeted physical examination could be performed <math>\pm</math> 30 minutes after the expected post-dose timepoint.
 
• Collect serum chemistry, hematology, urinalysis, and coagulation clinical laboratory samples at predose.
 
• Assess vital signs (blood pressure, heart rate, temperature, and respiratory rate) at predose and 1, 2, 4, 8, and 12 hours postdose. Vital signs will be obtained after the subject has been at rest in the supine position for at least 1 minute. The post-dose vital signs could be performed within 15 minutes earlier than the expected post-dose timepoints.
 
• Collect a standard 12-lead ECG in triplicate (5 minutes apart) at predose. The ECGs will be recorded after the subject has been supine and at rest for <math>\geq</math> 10 minutes prior to the first ECG and subjects will remain supine through the final ECG.
 
• Administer oral dose of RHEZ or IMP. RHEZ will be administered with 240 mL of still (noncarbonated) water 1 hour prior to a meal or 2 hours after a meal. The IMP will be administered with 240 mL of still (noncarbonated) water at room temperature.
 
• Provide breakfast, lunch, dinner, and an evening snack.
 
	
Day 8	

On Day 8, the following will be performed:
 
 
• Start overnight sputum collection for Day 8 sample (approximately 10 mL or more) at approximately 3:00 PM.
 
• Perform a targeted physical examination at predose and 4 hours postdose. The 4-hour post-dose targeted physical examination could be performed <math>\pm</math> 30 minutes after the expected post-dose timepoint.
 
• Assess vital signs (blood pressure, heart rate, temperature, and respiratory rate) at predose and 2 and 4 hours postdose. Vital signs will be obtained after the subject has been at rest in the supine position for at least 1 minute. The post-dose vital signs could be performed within 15 minutes earlier than the expected post-dose timepoints.
 
	

Protocol 323-201-00003

Table 3.7.3-1	Trial Days and Activities

 
Administer oral dose of RHEZ or IMP. RHEZ will be administered with 240 mL of still (noncarbonated) water 1 hour prior to a meal or 2 hours after a meal. IMP will be administered with 240 mL of still (noncarbonated) water at room temperature.
 
Provide breakfast, lunch, dinner, and an evening snack.
 
	
Day 9	
On Day 9, the following will be performed:	

 
End overnight sputum collection (for Day 8 sample) at approximately 7:00 AM. Sputum will be cultured on solid media for quantification of bacterial load and in the MGIT system for TTD determination, and assessed in the LAM assay.
 
Perform a targeted physical examination at predose and 4 hours postdose. The 4-hour post-dose targeted physical examination could be performed <math>\pm</math> 30 minutes after the expected post-dose timepoint.
 
Assess vital signs (blood pressure, heart rate, temperature, and respiratory rate) at predose and 2 and 4 hours postdose. Vital signs will be obtained after the subject has been at rest in the supine position for at least 1 minute. The post-dose vital signs could be performed within 15 minutes earlier than the expected post-dose timepoints.
 
Administer oral dose of RHEZ or IMP. RHEZ will be administered with 240 mL of still (noncarbonated) water 1 hour prior to a meal or 2 hours after a meal. The IMP will be administered with 240 mL of still (noncarbonated) water at room temperature.
 
Provide breakfast, lunch, dinner, and an evening snack.
 
	
Day 10	
On Day 10, the following will be performed:	

 
Start overnight sputum collection for Day 10 sample (approximately 10 mL or more) at approximately 3:00 PM.
 
Perform a targeted physical examination at predose and 4 hours postdose. The 4-hour post-dose targeted physical examination could be performed <math>\pm</math> 30 minutes after the expected post-dose timepoint.
 
Assess vital signs (blood pressure, heart rate, temperature, and respiratory rate) at predose and 2 and 4 hours postdose. Vital signs will be obtained after the subject has been at rest in the supine position for at least 1 minute. The post-dose vital signs could be performed within 15 minutes earlier than the expected post-dose timepoints.
 
Administer oral dose of RHEZ or IMP. RHEZ will be administered with 240 mL of still (noncarbonated) water 1 hour prior to a meal or 2 hours after a meal. The IMP will be administered with 240 mL of still (noncarbonated) water at room temperature.
 
Provide breakfast, lunch, dinner, and an evening snack.
 
	
Day 11	
On Day 11, the following will be performed:	

 
End overnight sputum collection (for Day 10 sample) at approximately 7:00 AM. Sputum will be cultured on solid media for quantification of bacterial load and in the MGIT system for TTD determination, and assessed in the LAM assay.
 
Perform a targeted physical examination at predose and 4 hours postdose. The 4-hour post-dose targeted physical examination could be performed <math>\pm</math> 30 minutes after the expected post-dose timepoint.
 
Assess vital signs (blood pressure, heart rate, temperature, and respiratory rate) at predose and 2 and 4 hours postdose. Vital signs will be obtained after the subject has been at rest in the supine position for at least 1 minute. The post-dose vital signs could be performed within 15 minutes earlier than the expected post-dose timepoints.
 
Administer oral dose of RHEZ or IMP. RHEZ will be administered with 240 mL of still (noncarbonated) water 1 hour prior to a meal or 2 hours after a meal. The IMP will be administered with 240 mL of still (noncarbonated) water at room temperature.
 
Provide breakfast, lunch, dinner, and an evening snack.
 
	

Protocol 323-201-00003

Table 3.7.3-1	Trial Days and Activities
Day 12	
On Day 12, the following will be performed:	
